Upload any additional documents that may be related to this study

Title Page:

Grant: Multicenter Trial of Combined Pharmacotherapy to Treat Cocaine Dependence
IRB# 6698

PI: [name] M.D.^{1,2}

1. New York State Psychiatric Institute, Division of Substance Abuse¹
[name]
[name]
USA

2. Department of Psychiatry, College of Physicians and Surgeons of Columbia University²
[name]
[name]
USA

Data Analysis created on January 1, 2018

Funding Source: Funding for this work was provided by NIDA.

Trial Registration: clinicaltrials.gov Identifier: NCT01811940

Data Analysis

The primary outcome was a dichotomous measure of a clinically meaningful treatment response, defined as three consecutive weeks of abstinence (no cocaine use based on self-report confirmed by urine toxicology) at the end of the 12-week medication phase of the trial. Secondary outcomes were (1) dichotomous measure of at least 3 consecutive weeks of abstinence during the study, (2) dichotomous longitudinal, weekly status of cocaine use determined by urine toxicology samples per subject, positive status occurs if at least one urine sample was positive for benzoylecgonine, (3) continuous longitudinal, symptoms of cocaine withdrawal as measured by the Cocaine Selective Severity Assessment (CSSA) assessed at week 6,10, and 14, (4) continuous longitudinal, weekly cocaine cravings as measured by the Brief Substance Craving Scale (BSCS), and (5) survival, time to dropout.

The dichotomous primary and secondary outcome (1) was analyzed using either exact or conventional logistic regressions with predictor treatment (MAS-ER and topiramate vs. placebo), and covariates: site (binary, UPENN vs. CUMC) and baseline severity of cocaine use (continuous, total number of cocaine use days in the 28 days prior to randomization). Secondary outcomes (2) – (4) were analyzed using longitudinal mixed effect models with logit link function for binary outcomes and linear link functions for continuous outcomes. Times to dropout (5) were compared using Kaplan-Meier curves and log-rank statistics.

All analyses were conducted in SAS® and on the intent-to-treat sample of all randomized patients. All statistical tests were 2-tailed at a significance level of 5%, unless otherwise stated.

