This study was a collaborative study between the Substance Treatment and Research Service (STARS) and the University of Pennsylvania (UPenn) with one uniform screening and study procedure. In total, 169 individuals were enrolled, 127 were randomized, and 83 (65%) completed the study. Of the individuals enrolled at the STARS site, 89 participants were enrolled, with 68 being randomized. Thirty-seven participants (54%) completed the 14-week treatment trial. The retention is what is expected in this population and kept us on track for investigating both the primary and secondary aims of the investigation. Patients on average experienced the study as helpful and informative. The study procedures were well tolerated by participants. We are working on cleaning the data for analysis.

Funding

Have there been any changes in funding status since the prior approval?

No

Have the principal investigator and other investigators made all required disclosures of financial interest in the study sponsor/product?

Yes

Summary

Have there been any study findings, recent literature, or untoward events occurring here or at other sites in the past year which might affect the analysis of the safety, risks or benefits of study participation?

No

Have there been any serious adverse events (serious and/or unanticipated problems involving risks to subjects or others at this site which occurred in the past year)?

No

Have all study staff with a significant role in the design or implementation of the human subject components of this study received required training in human research subject protections?

Yes

Is the study covered by a certificate of confidentiality?

Yes

Certificate expiration date (mm/dd/yyyy)

12/31/2021

Overall Progress

Approved sample size

99

Total number of participants enrolled to date

89

Number of participants who have completed the study to date

37

Have there been any significant deviations from the anticipated study recruitment, retention or completion estimates?

No

Comments / additional information

Sample Demographics

Specify population

cocaine dependent adults

Total number of participants enrolled from this population to date

89

Gender, Racial and Ethnic Breakdown

Seventy-one (80%) out of 89 subjects enrolled for this study were male, 18 (20%) were Caucasian, 36 (41%) were African-American, 24 (27%) were Hispanic, 3 (3%) were Asian, 2 (2%) were Native American, and 6 (7%) were Other.

Summary of Current Year's Enrollment and Drop-out

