b) **Urine Riboflavin:** A patients' compliance with respect to study medication will be monitored in two ways, by presence of riboflavin and pill count. The presence of riboflavin in a patients urine samples will be checked three times per week; the urine samples will be examined for riboflavin which will signify the consumption of the study capsules. The absence of riboflavin in a patient's urine will not result in termination of a patient's involvement in the study. Secondly, medication compliance will be monitored by pill count on the medication bottles returned by the patient.

You can upload charts or diagrams if any

Criteria for Early Discontinuation

Criteria for Early Discontinuation

Removal from the Study for Worsening of Substance Abuse: Participants whose substance abuse significantly worsens during the course of treatment will be removed and treated clinically. If necessary, a referral for inpatient treatment will be made. This involves clinical judgment on the part of the treating

psychiatrist(s) who are experienced with this population. This does not include transient modest worsening of drug use since substance dependence is a chronic relapsing condition. If more intensive treatment is deemed necessary, the participant will be offered continued weekly meetings with the physician until an appropriate referral can be made.

Drop-out criteria during the screening and study period include:

- 1) If the patient develops serious psychiatric symptomatology (weekly psychiatric evaluation, CGI ≥ 6 [much worse than baseline] for two consecutive weeks).
- 2) If the patient develops signs of cardiovascular instability (weekly vital signs and clinical evaluation; pulse at rest > 100 or BP at rest $> 140/90$ mm Hg for more than 2 weeks or SBP > 160 , DBP > 110 , sitting quietly HR > 110 on any visit will result in immediate discontinuation of study medications.)
- 3) Cardiac risks as defined as chest pains, fainting or arrhythmias.
- 4) If the patient's continued cocaine use, even if improved from baseline, places them at risk for self-destructive behavior or otherwise places them at significant risk (weekly clinical evaluation; CGI ≥ 6 [much worse than baseline] for two consecutive weeks).
- 5) If the subject becomes pregnant (monthly urine pregnancy testing).

Blood and other Biological Samples

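### Does the SAP leave open how the 44 of 127 randomised patients who did not complete are scored on the primary outcome?

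*SAP*

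**What the plan says.** The SAP is one page. Under Data Analysis it makes the primary outcome dichotomous: "three consecutive weeks of abstinence (no cocaine use based on self-report confirmed by urine toxicology) at the end of the 12-week medication phase". The model is exact or conventional logistic regression on treatment, site and baseline days of cocaine use. All analyses are run "on the intent-to-treat sample of all randomized patients".

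Secondary outcome (2) is weekly cocaine status from urine, where "positive status occurs if at least one urine sample was positive for benzoylecgonine". It is analysed with a longitudinal mixed model with a logit link. Dropout itself appears only as secondary outcome (5), time to dropout, compared by Kaplan-Meier curves and the log-rank test. No imputation method or missing-data sensitivity analysis is named.

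The progress summary that opens the Protocol reports retention: "In total, 169 individuals were enrolled, 127 were randomized, and 83 (65%) completed the study". For the STARS site, with 68 randomised, it adds: "Thirty-seven participants (54%) completed the 14-week treatment trial". It comments: "The retention is what is expected in this population and kept us on track for investigating both the primary and secondary aims".

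On reasons for leaving, the Protocol's Criteria for Early Discontinuation states: "Participants whose substance abuse significantly worsens during the course of treatment will be removed and treated clinically". The same section lists cardiovascular instability among the drop-out criteria.

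**The concern.** The primary outcome is read in a fixed late window, and about a third of the randomised patients did not finish. Many of them will have no urine or self-report there. An intent-to-treat statement fixes who is analysed but not what value a patient without data receives, and standard logistic regression software silently drops records with no outcome. If that default were followed, the analysis would become one of completers.

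Leaving is also unlikely to be neutral. Removal for worsening use is tied to the outcome, and removal for cardiovascular reasons may differ between a stimulant-containing arm and placebo. Completion differs sharply by site. Secondary outcome (2) can be read as letting a week with few samples count as negative, which would sit oddly beside a primary outcome that demands confirmation. If the scoring rule were truly open, it could be picked after the data were seen, and the primary result might depend on the pick.

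**Working it through.** **1. The stated retention figures.** Overall: 83/127 = 65.4%, which matches the stated 65%. STARS: 37/68 = 54.4%, which matches 54%.

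**2. Non-completers.**
- Overall: 127 − 83 = 44 (44/127 = 34.6%).
- STARS: 68 − 37 = 31 (31/68 = 45.6%).
- UPenn, by subtraction in a two-site trial: 127 − 68 = 59 randomised, 83 − 37 = 46 completed, so 13 did not (13/59 = 22.0%).
- Site difference: 45.6 − 22.0 = 23.6 points; Newcombe 95% CI 7.0 to 38.2; Fisher P = 0.008.

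**3. Is 44 the number without a primary outcome?** Not exactly. Completion refers to the 14-week trial. The Protocol's Design Overview puts the lead-in in week 1, maintenance through week 13 and the taper in week 14. The 12-week medication phase is then weeks 2 to 13, and its last three weeks are 11 to 13. A patient who left in week 14 is a non-completer with a full window. A completer can also have missed visits inside it. So 44 is an approximation, and may be too high.

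**4. What value does a leaver get?** Set the two SAP statements side by side. Response requires abstinence confirmed by urine over three consecutive weeks. Everyone randomised is in the analysis. A leaver has no confirmation, so does not meet the definition, and may not be left out. Non-responder is the simplest value that satisfies both statements. Dropping the record satisfies the first and breaks the second.

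**5. How much could the rule matter?** The documents give no completion by arm, so the following is illustration: arms of 64 and 63, all 44 missing, response rates among completers assumed, P-values from unadjusted logistic regression (Wald).

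| Leavers, active / placebo | Assumed completer response | Leavers as non-responders | Completers only |
|---|---|---|---|
| 22 / 22 | 30% v 10% | 13/64 v 4/63, P = 0.028 | 13/42 v 4/41, P = 0.022 |
| 27 / 17 | 30% v 10% | 11/64 v 5/63, P = 0.12 | 11/37 v 5/46, P = 0.036 |
| 17 / 27 | 30% v 15% | 14/64 v 5/63, P = 0.034 | 14/47 v 5/36, P = 0.094 |

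The verdict changes in the second and third rows. Both need a gap of ten leavers between arms, and the assumed response rates differ between them. With rates held at 30% and 10%, there is no change of verdict when 17 to 25 of the 44 leave the active arm. At 30% and 15% there is none when 18 to 32 do. Other assumed rates cross more often: at 35% and 15% the verdict changes in 12 of 21 splits examined. The balanced row keeps its verdict, although the risk difference moves from 14.0 to 21.2 points. In every row the last column is an analysis that the SAP's analysis set does not allow.

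**6. No-assumption bounds.** With equal arms of 63.5, the width is missing/63.5: 44/63.5 = 69.3 points, or 30/63.5 = 47.2 points if 30 are missing. These bounds let a patient removed for worsening use count as abstinent, so they describe what is logically possible and not a plausible range.

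**7. Secondary outcome (2).** The SAP says a week is positive if a sample is positive. It does not say a week without samples is negative. In a mixed model such a week can simply be unobserved. What remains unstated is the coding of a week with some of its three samples missing.

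**The case for a change.** The strongest opposing case is that an implied rule is not a stated one. The SAP never says that missing means not abstinent, nor how a single missed sample within a confirmed week is treated. The Protocol itself calls this level of dropout expected, and its reference list holds papers on informative dropout that the SAP does not use. A few sentences and one sensitivity analysis on data already collected would cost little.

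Part of this stands. There is no explicit missing-data sentence, and the coding of partly sampled weeks is left to the analyst in both the primary outcome and secondary outcome (2). Scoring leavers as non-responders also has a price: the effect becomes partly an effect on retention. That is a known trade-off for an abstinence endpoint, and time to dropout is analysed separately as secondary outcome (5).

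The rest is weaker. The rule the concern would have written in is the one the outcome definition already yields. A sensitivity analysis would be informative but would replace no stated method and leave the primary result as it is. Patients removed for worsening use are treatment failures, so non-responder scoring suits them. Unequal dropout by site does not by itself bias the treatment comparison, because randomisation is stratified by site and site is in the model. Nor does judging the retention statement depend on a scoring rule: the Protocol's 62 required completers (Description of Subject Population) can be set directly against the 37 at STARS.

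**Conclusion.** The counts are right and the missing sentence is real, but this is a gap that an analyst following the SAP fills sensibly and in one direction. The outcome definition and the all-randomised analysis set together make an unconfirmed patient a non-responder, so all 127 have a value. The feared reversal of the primary result requires an analysis the SAP excludes, together with dropout by arm and response rates that the documents do not give. About 44 patients (35%) are affected at most by the reading of non-completion used here, and probably fewer, since leaving in week 14 does not cost the window.

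This conclusion rests on taking confirmation by urine at its plain meaning and the intent-to-treat statement as binding. It would not hold if the trial were reported on completers only, but that would depart from the SAP. Writing the rule down, tabulating missing outcomes by arm and adding a sensitivity analysis are good reporting practice; none of them alters the planned primary analysis, so no change to the plan is called for.

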Single-Blind PBO Lead-In Phase: Participants who meet inclusion criteria and who sign informed consent will be placed on placebo, under single-blind conditions for a 1-week period (Days 1-7). The placebo lead-in phase will allow us to enter only those participants who have demonstrated a commitment to the study by attending the required study visits during the first week of treatment. Additionally, the placebo lead-in phase will allow us to assess if some participants are able to significantly decrease their cocaine use during the first week of the study. Individuals will be stratified by the site (Columbia versus University of Pennsylvania) and the presence of an alcohol use disorder. The purpose of the stratification is to distribute these potential prognostic factors equally across treatment groups. To the extent that these stratification variables are predictive of outcome, stratifying by them should enhance statistical power to test treatment effects (Fleiss et al 1986).

Randomization: Those patients randomized to the placebo group will continue to receive placebo throughout the treatment. Patients randomized to the MAS-ER/topiramate group will begin receiving both medications at the start of week 2 and will receive a stable dose of MAS-ER by study week 4 and topiramate by week 8.

Dosing Schedule: Subjects will take capsules (PBO or ER-MAS/topiramate) as titrated in Table 2 below.

Medication Lead-out: During week 14 patients assigned to active medication have their medication tapered. The purpose of the placebo lead-out is to keep patients blind to the exact point of medication discontinuation, and afford systematic observation of effects of medication discontinuation.

26 Week Outcome: Twelve weeks after study completion (26 weeks after enrollment) an attempt will be made to evaluate all participants to explore whether there may be effects of treatment that endure or emerge after medication discontinuation. In exploratory analyses, outcome at 26 weeks will be compared between groups originally assigned to medication or placebo on the main primary and secondary outcomes listed above and on Addiction Severity Index composite scores.

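### Randomisation is stratified by site and alcohol use disorder, but the logistic models omit alcohol use disorder and the dropout log-rank names no strata, which gives up a little power

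*SAP*

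**What the plan says.** The protocol's General Design section, under Single-Blind PBO Lead-In Phase, sets two randomisation strata: "Individuals will be stratified by the site (Columbia versus University of Pennsylvania) and the presence of an alcohol use disorder". It gives two reasons. The first is balance: "The purpose of the stratification is to distribute these potential prognostic factors equally across treatment groups". The second is efficiency: "To the extent that these stratification variables are predictive of outcome, stratifying by them should enhance statistical power to test treatment effects".

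The SAP's Data Analysis section says the primary outcome and secondary outcome (1) "was analyzed using either exact or conventional logistic regressions", with treatment as predictor and "covariates: site (binary, UPENN vs. CUMC) and baseline severity of cocaine use" (use days in the 28 days before randomisation). Alcohol use disorder appears nowhere in the SAP, and no reason for leaving it out is given. For the fifth secondary outcome the SAP says only: "Times to dropout (5) were compared using Kaplan-Meier curves and log-rank statistics". It names no strata or covariates there, so that test uses neither randomisation factor.

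**The concern.** Stratified randomisation balances a prognostic factor between arms, but most of the precision gain is collected only when the analysis also uses the factor. Otherwise its variation stays in the error term. The treatment comparison then varies less from trial to trial than the test assumes, so the test tends to be conservative and loses power.

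The SAP uses one of the two factors in the logistic models and neither in the log-rank. The stake is efficiency, not validity: in a trial of 127 patients some power is given up that the design had already paid for.

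**Working it through.** **Inputs from the documents.** The protocol's progress summary reports: "In total, 169 individuals were enrolled, 127 were randomized, and 83 (65%) completed the study". For the Columbia site it reports 89 enrolled, "with 68 being randomized. Thirty-seven participants (54%) completed the 14-week treatment trial". The SAP sets two-sided 5% tests on all randomised patients. The documents state no power figure for this comparison, so there is none to reproduce.

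**Is site related to dropout?** By subtraction, taking completion to mean the same in both counts:

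- other site, randomised: 127 − 68 = 59
- other site, completed: 83 − 37 = 46
- completion: 37/68 = 54.4% against 46/59 = 78.0%, a gap of 23.5 points
- Fisher's exact test: p = 0.0085
- under a constant dropout hazard at each site, the implied hazard ratio is ln(0.544)/ln(0.780) ≈ 2.4

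Site is therefore clearly associated with the outcome that the log-rank tests.

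**Primary logistic model.** The documents give neither the prevalence nor the effect of alcohol use disorder (AUD), so both are assumed. Assumptions: 68 + 59 patients, blocks of 4 within site by AUD, treatment odds ratio (OR) 3, control response 10% or 15%, AUD prevalence 40% (20% also run at 15% response), site OR 1.5, baseline days uniform on 9 to 28 with OR 0.92 per day. Each scenario has 6,000 trials. The likelihood-ratio test of treatment, adjusted for site and baseline days, is run with and without AUD on the same data.

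| Assumed AUD OR | Change in power from adding AUD | Example |
|---|---|---|
| 1 | +0.1 to +0.3 points | – |
| 0.4 | +0.7 to +1.3 points | 70.1% to 71.3% |
| 0.2 | +1.9 to +2.9 points | 65.6% to 68.5% |

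The Monte Carlo standard error (SE) of each difference is at most 0.25 points. With no treatment effect (15% response, 40% prevalence), size is 4.8–5.7% without AUD and 5.4–5.9% with it (SE 0.3), so part of the gain reflects size.

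A second simulation used response of 20% vs 40%, an OR of 1.5 per SD of baseline use, AUD prevalence 40%, and AUD odds ratios against response of 1, 1.5, 2, 3 and 4 (4,000 trials each). Power rose by 0.3, 0.4, 1.0, 2.1 and 2.2 points. At 10% vs 30% the gains were 0.1 to 1.6 points. Monte Carlo error was about 0.7 points per power figure.

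**Exact option.** Conditioning on site and AUD rather than site alone, with baseline days left out (3,000 trials per scenario), changed power by +0.1 points at AUD OR 1, +0.6 to +1.3 at 0.4 and +1.9 to +3.0 at 0.2 (SE at most 0.32).

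**Log-rank.** The statistic is U²/V, with U the sum of observed minus expected events in one arm and V its variance. The stratified version sums U and V within strata. Assumptions: weekly dropout over 13 post-randomisation weeks, site hazards set so that completion averages 37/68 and 46/59, AUD prevalence 40%, AUD hazard ratio (HR) 1 to 2, 20,000 trials per scenario.

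| | Unstratified | Site by AUD |
|---|---|---|
| Size | 4.0–4.3% | 5.1–5.2% |
| Power, treatment HR 0.6 | 33.7–36.2% | 38.5–38.8% |
| Power, treatment HR 0.45 | 69.0–71.1% | 73.3–73.6% |

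Within scenarios the gain is 2.2 to 4.8 points (SE at most 0.18).

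**Which stratum supplies the gain?** The same set-up with site alone added (4,000 trials per cell, treatment HR 0.6) gives:

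| AUD HR | Unstratified | Site only | Site by AUD |
|---|---|---|---|
| 1 | 35.9% | 38.6% | 38.6% |
| 1.5 | 35.6% | 38.5% | 39.0% |
| 2 | 33.7% | 36.1% | 38.3% |

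Site supplies all or most of the gain up to an AUD HR of 1.5. At 2 the gain is shared about equally.

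**The case against.** The strongest reply is that the primary analysis barely changes. The logistic models already include site and baseline use, every AUD input is assumed, and the protocol calls the factors only potentially prognostic. A gain of 2 to 3 points needs an odds ratio as strong as 0.2, and part of the likelihood-ratio gain reflects slightly higher size. All of this stands and limits the primary-outcome point to a small one.

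The site completion counts are evidence about site, not AUD. That also stands: the documents themselves support stratifying the log-rank by site, while AUD's contribution is conditional. Dropout is also the last-listed secondary outcome, and none of the protocol's five hypotheses concerns it.

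The exact-test result comes from a model without baseline days, so it shows no power cost only for that reduced model. With very few responders (3–5% control response, assumed), adding AUD moved likelihood-ratio power by only 0.3 to 1.0 points, while size was 8–10% with or without it. In that setting the choice between the exact and conventional methods matters far more than this covariate.

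None of this gives a reason to leave the strata out. None of the scenarios showed a material power loss from using them, and the protocol's own rationale for stratifying points to using them.

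**Conclusion.** The concern holds as a modest loss of efficiency. The analysis does not follow the randomisation: AUD is missing from the two logistic models, and the log-rank names neither factor. Type I error is not inflated by the omission.

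For the primary test the loss is negligible if AUD does not predict response, around 1 point for a moderate effect and about 2 to 3 points for a strong one. These sizes rest wholly on assumed AUD prevalence and effect. For dropout the unstratified test is slightly conservative (about 4% against a nominal 5%) and loses 2.2 to 4.8 points of power when site hazards match the reported completion. The site part of that loss rests on the protocol's own counts. The change is worth making because it is nearly free, not because the planned conclusions are unsafe.

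**What to change.** - Add the alcohol use disorder stratum as a covariate in the logistic models for the primary outcome and secondary outcome (1).
- Stratify the dropout log-rank by site and alcohol use disorder. Site is the stratum with direct support in the documents.
- Date the change. The SAP is dated January 2018 and written in the past tense. If the planned analysis has already been run, keep it as the main result and report these as labelled sensitivity analyses. Apply the same label if the change is made after unblinded results were seen.

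The cost is one covariate in two models and one strata statement. No new data are needed, because alcohol use disorder status had to be known in order to randomise.
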